### **Patients in the ITV Injection Treatment (Control) Arm**

Patients will receive their first ITV injection of 50  $\mu$ L of the 10-mg/mL ranibizumab (0.5 mg dose) formulation at the Day 1 visit, which may occur (if feasible) at the conclusion of the randomization visit. Afterwards, patients will receive monthly ITV injections of 50  $\mu$ L of 10-mg/mL formulation. Patients will be receiving the study treatment at each scheduled monthly visit until the study treatment completion (see Section 3.2 for the definition). Missed treatments will not be made up.

Study visits for the ITV treatment arm will be scheduled to occur according to the schedule in Appendix 2 and have to be relative to the Day 1 (the first study treatment) visit date until patients complete the study.

Ranibizumab dosing should not occur earlier than 22 days after the previous dosing. Guidelines for treatment interruption or discontinuation are provided in Section 5.1.1.1 and Table 6.

### **Pre-Screening**

Pre-screening is available for newly diagnosed nAMD patients who are treatment naïve in the study eye. Patients eligible for the pre-screening will receive their first ITV injection of 50  $\mu$ L of the 10-mg/mL ranibizumab (0.5 mg dose) formulation at the Pre-Screening visit 1, and their second injection  $30 \pm 7$  days later (Pre-Screening visit 2). A third pre-screening treatment may be allowed after consultation with the Medical Monitor. Afterwards, patients will undergo the screening visit, which will occur at least 7 days following administration of the last pre-screening ITV ranibizumab treatment to the study eye (see Appendix 3).

## **Run-In**

Run-in is available for patients diagnosed with nAMD in the study eye within 9 months prior to screening who have been treated with a single anti-VEGF ITV injection, or with no more than eight anti-VEGF ITV injections and with the most recent dose being aflibercept or bevacizumab. Patients eligible for the run-in treatment will receive their single ITV injection of 50 µL of the 10 mg/mL ranibizumab (0.5 mg dose) formulation in the study eye at the time of consent. In exceptional cases, a second run-in treatment may be allowed after consultation with the Medical Monitor. Afterwards, patients will undergo the screening visit, which will occur at least 7 days following administration of the run-in ITV ranibizumab treatment to the study eye (see [Appendix 4](#)).

### **4.3.2.3 Administration Implant Treatment Arms**

Prior to Implant insertion or explantation, patients will be required to verify that they have self-administered antimicrobial eye drops to the study eye 4 times within the previous 24 hours. As per investigator's discretion, patients may also be required to have self-administered antimicrobial eye drops to the study eye 4 times within the 24 hours prior to potential Implant refills.

All patients must be instructed to self-administer antimicrobial eye drops to the study eye 4 times daily for 3 days following any refills. Antimicrobial eye drops to the study eye will also be required 4 times daily for 7 days following Implant insertion and explantation.

All patients randomized to the Implant arm and receiving ongoing aspirin or NSAID treatment must interrupt aspirin or NSAID treatment 7 days prior to Implant insertion or explantation and until at least the Day 2 safety visit following the procedure.

Prior to and during the Implant insertion procedure, blood pressure must be controlled. Before surgery, blood pressure must be checked after the patient has been in a resting state (i.e., supine or sitting) for at least 15 minutes. If blood pressure exceeds the recommended levels (i.e., between 100/60 mmHg and 155/95 mmHg), the Implant insertion surgery must be rescheduled.

Patients in the Implant treatment arms will have the Implant, prefilled with ranibizumab, surgically inserted into the study eye at the Day 1 visit and subsequently refilled at monthly visits only if the protocol-specified refill criteria are fulfilled (see Section [3.1.1](#)). The insertion and explantation procedures must be performed in the surgery room while the refill procedure is permitted in the physician office setting. For detailed instructions on the Implant initial fill, insertion, refill, and explantation procedures, refer to the RPDS IFU.

## **ITV Injection Arm**

Patients' self-administered antimicrobial treatments will be prescribed at the investigator's discretion. Prior to the monthly ITV injections, patients who are prescribed antimicrobials will be required to verify that they have self-administered their antimicrobials eye drops to the study eye pre- and post-injection. For detailed instructions on pre-injection preparation, administering the ITV injection, and post-ITV injection procedures for the study eye, consult [Appendix 7](#) to [Appendix 9](#).

Guidelines for dosage modification and treatment interruption or discontinuation are provided in Section [5.1](#).

## **All Treatment Arms**

Adverse events associated with an overdose or incorrect administration of ranibizumab should be recorded on the Adverse Event electronic Case Report Form (eCRF).

## **ITV Injection of Open-Label Ranibizumab**

Patients' self-administered antimicrobial treatments will be prescribed at the investigator's discretion.

### **4.3.2.4 Storage**

#### **4.3.2.4.1 Ranibizumab Port Delivery System**

**Ranibizumab.** Vials of ranibizumab are for single use only. A vial used for one patient must not be used for any other patient.

Upon receipt, study drug kits must be refrigerated at 2°C to 8°C (36°F to 46°F). Sites must monitor and record refrigerator temperature at all times (24 hours per day, 7 days per week). **DO NOT FREEZE.** Vial content should not be frozen or shaken and should be protected from direct light. **Store in original carton before and after use.**

**RPDS.** Each Implant is held by an Insertion Tool and is packaged inside a sterile barrier system pouch. The Initial Fill Needle and Explant Tool are each packaged separately in a sterile barrier pouch system. The Refill Needles are packaged separately and individually in a tray. The Implant, Insertion Tool, Initial Fill Needle, Refill Needle, and Explant Tool should be maintained at a room temperature of 15°C to 30°C (59°F to 86°F). The storage location at the clinical site must have restricted access and be available only to study personnel. The Implant, Initial Fill Needle, Insertion Tool, and Explant Tool are supplied sterilized by exposure to ethylene oxide. The Refill Needles are sterilized by e-beam.

**DO NOT RESTERILIZE.**

The RPDS components (see [Table 1](#)) must not be resterilized because of the possibility of damaging the mechanical integrity of the Implant and ancillary devices.

The packages should be opened only immediately prior to use.

DO NOT USE if the package is damaged, punctured, or broken as sterility may be compromised. Do not use beyond the expiration date.

#### **4.3.2.4.2 Investigational Medicinal Product and RPDS Accountability**

All investigational medicinal products (IMPs) (ranibizumab) and RPDS required for completion of this study (including all the components of the RPDS, see [Table 1](#)) will be provided by the Sponsor. The investigational site will acknowledge receipt of IMPs using the IxRS to confirm the shipment condition and content. Any damaged shipments will be replaced.

RPDS (Initial Fill Needle, Refill Needle with its content, explanted Implant with its remaining content, Explant Tool, and Insertion Tool) must be returned to the Sponsor or Sponsor's designee with the appropriate documentation.

In order to ensure traceability, each device component of the RPDS will be identified by a batch number.

Accurate records of all IMPs and RPDS received at, dispensed from, returned to, and destroyed and/or disposed of by the study site should be recorded on the Drug and RPDS Inventory Logs. See the Study Manual for further details.

IMPs (used, damaged drug kits) will either be disposed of at the study site according to the study site's institutional standard operating procedure or returned to the Sponsor with the appropriate documentation. The site's method of IMP destruction must be agreed to by the Sponsor. The site must obtain written authorization from the Sponsor before any IMP is destroyed. IMP destruction must be documented on the appropriate form. See site Pharmacy binder for further details.

#### **4.3.2.4.3 Ranibizumab (Non-Study Eye)**

At the discretion of the evaluating investigator, study patients may receive ITV injection of ranibizumab for their fellow (non-study) eye. The drug will be open-label ranibizumab and will be supplied by the Sponsor. If a change in therapy is clinically indicated for the fellow eye per investigator judgment, the change must be discussed and agreed with the Medical Monitor prior to being made.

#### **4.3.2.4.4 Open-Label Ranibizumab**

The drug will be open-label ranibizumab and will be supplied by the Sponsor.

### **4.4 PRODUCT QUALITY ASSESSMENTS**

#### **4.4.1 Ranibizumab in Contents Retrieval from Implant**

##### **4.4.1.1 Explanted Implants with Contents**

Following explantation, the Implants containing a mixture of ranibizumab drug product (along with the vitreous components, which may have diffused into the Implant) will be preserved and forwarded by the site to the Sponsor or Sponsor selected designee for

potential future analysis. A method to retrieve the contents from explanted Implants is in place and protocols to characterize drug product are under development. In addition, the explanted Implants may undergo physical inspection and/or functional testing.

#### **4.4.1.2 Ancillary Devices**

The Initial Fill Needle, Insertion Tool, Refill Needle, and Explant Tool must be returned to the Sponsor or Sponsor's designee for possible physical inspection and/or functional testing.

#### **4.4.2 Continued Access to RPDS**

Currently, the Sponsor does not plan to provide ranibizumab via Implant or via ITV injections or to provide other study interventions to patients after the conclusion of the study or following early patient withdrawal. The Sponsor will evaluate the appropriateness of continuing to provide ranibizumab treatment to Implant treatment arms patients after evaluating RPDS efficacy, safety, and PK data gathered in the study. Depending on the results of the study, the Sponsor may offer study patients in the Implant arms entry into a separate RPDS *Extension* Study to continue to provide ranibizumab via the Implant in an open-label manner. If the results from this trial do not warrant further investigation of the RPDS, all patients in the Implant arms will have their Implants explanted.

### **4.5 CONCOMITANT THERAPY**

#### **4.5.1 Permitted Therapy**

Concomitant medications are any prescription drugs or over-the-counter preparations other than protocol-specified procedural medications (e.g., dilating drops, fluorescein dyes, cefazolin or vancomycin, or medications associated with Implant insertion, refill, and extraction procedures) and pre- and post-study treatment medications (e.g., proparacaine, antimicrobials, steroids) used by a patient within 7 days preceding the randomization visit until conclusion of the patient's study participation or early termination visit.

Patients who use other maintenance therapy should continue its use unless prohibited as indicated in Section 4.5.2. All concomitant medications should be reported to the investigator and recorded on the appropriate eCRF:

- Following randomization, if a patient's fellow eye requires treatment for nAMD, treatment with ITV ranibizumab injection may be administered at the discretion of the evaluating investigator. If a change in therapy is clinically indicated for the fellow eye per investigator judgment, the change must be discussed and agreed with the Medical Monitor prior to being made.
- All patients randomized to the Implant arm and receiving ongoing aspirin or NSAID treatment must interrupt aspirin or NSAID treatment 7 days prior to implant insertion or explantation. These medications can be restarted, if appropriate, after the Day 2 safety visit.

- As per investigator discretion, the Implant arms patients who had the Implant explanted may receive ITV ranibizumab for their study eye treatment.
- Cataract surgery in the study eye may be performed if clinically indicated and should occur 7 or more days after the last study treatment; the next study treatment will be held for 28 or more days following the surgery. At least one study treatment (e.g., monthly ITV injection treatment arm) may be missed after cataract surgery is performed.
- The onset of increased IOP and/or glaucoma in the study eye during a patient's study participation should be treated as clinically indicated.
- Use of topical steroids post-implant insertion or post-explantation surgery in the study eye is permitted.
- In a limited fashion, intra-articular or intramuscular corticosteroids may be allowed after consultation with the Medical Monitor.

#### **4.5.2 Prohibited Therapy**

At the discretion of their physician, patients may continue to receive all medications and standard treatments administered for other conditions except in the following instances:

- Concurrent use of any systemic anti-VEGF agents
- Concurrent use of oral corticosteroids (prednisone > 10mg/day or equivalent)
- Concurrent study eye treatment for nAMD with anti-VEGFs other than the study drug treatment
- Concurrent fellow eye treatment for nAMD with anti-VEGFs other than ranibizumab. If a change in therapy is clinically indicated for the fellow eye per investigator judgment, the change must be discussed and agreed with the Medical Monitor prior to being made.
- Concurrent treatment with focal laser photocoagulation for nAMD in the study eye
- Concurrent treatment with Visudyne® for nAMD in either eye
- Concurrent use of ITV or subtenon corticosteroids in the study eye
- Concurrent use of and participation in other experimental therapies (except those with minerals and vitamins) are not allowed.

Note: If patients receive the above listed treatments at any time during the study, the Sponsor will determine if discontinuation of the study treatment is required.

- Concurrent use of anticoagulants, antiplatelets (other than aspirin), or medications known to exert similar effects are prohibited at study entry, but may be initiated after the Day 14 safety visit if medically necessary and in consultation with the Medical Monitor. Oral anticoagulants include vitamin K antagonists (e.g., warfarin), direct factor Xa inhibitors (e.g., rivaroxaban, apixaban, edoxaban, fondaparinux), and direct thrombin inhibitors (e.g., dabigatran). Antiplatelet therapies include clopidogrel, prasugrel, dipyridamole, ticagrelor, and ticlodipine.

- Concurrent use of aspirin or NSAID at both the time of Implant insertion and explantation procedure (see Section 4.5.1 and Section 4.3.2.3 for aspirin and NSAID interruption requirements)
- Use of magnetic resonance imaging (MRI) scans for patients in the Implant treatment arms is conditional. Investigators should discuss with the Medical Monitor if MRI use is required prior to this procedure being performed. For additional information refer to RPDS IFU.

## **4.6 STUDY ASSESSMENTS**

### **4.6.1 Medical History, Concomitant Medication, and Demographic Data**

Medical history includes clinically significant diseases, surgeries, smoking history, and use of alcohol.

All medications (e.g., prescription drugs, over-the-counter drugs, herbal/homeopathic remedies, nutritional supplements) other than protocol-specified procedural medications (e.g., dilating drops, fluorescein dyes, cefazolin or vancomycin, Implant insertion, refill and extraction procedures medications, and pre- and post-treatment medications [e.g., proparacaine, antimicrobials, steroids]) used by the patient within 7 days prior to the randomization visit until the study completion will be recorded on the eCRF concomitant medication log.

Demographic data will include age, sex, and self-reported race/ethnicity.

### **4.6.2 Vital Signs**

Vital signs will include measurements of pulse and systolic and diastolic blood pressure obtained with the patient in a seated position after resting for 5 minutes. Height and weight will also be recorded at screening. At visits when a patient receives study treatment, vital signs will be measured pre-treatment.

### **4.6.3 Physical Examinations**

A targeted physical examination should include an evaluation of the head, eyes, ears, nose, throat, and cranial nerves. A patient's height and weight will be recorded as well. If any abnormalities are noted during the study, the patient may be referred to another doctor.

Changes from baseline abnormalities should be recorded in patient notes. New or worsened clinically significant abnormalities should be recorded as adverse events on the Adverse Event eCRF.

#### **4.6.4            Ocular Assessments**

Except where noted, all ocular assessments should be performed for both eyes:

- BCVA on ETDRS chart at a starting distance of 4 m (perform prior to dilating eyes; see [Appendix 10](#))
- BCVA on ETDRS chart under low luminance conditions at a starting distance of 4 m (perform prior to dilating eyes; see [Appendix 11](#))
- The following measurement will be performed in both eyes of the patients in the Implant treatment arms, from sites that have ultrasound or optical biometry, and will be recorded on the appropriate eCRF:
  - Axial length measurement (ultrasound or optical biometry)
- IOP measurement
  - At each monthly visit, perform IOP measurement prior to dilating eyes or procedure; the method used for a patient must remain consistent throughout the study for visits in the office
  - Before Implant insertion or explantation surgery, the treating physician must check IOP for the study eye using Tono-Pen tonometry.
  - Upon completion of the Implant insertion or explantation surgery, the treating physician must check IOP for the study eye only by digital palpation before patching the eye.
- Slit lamp examination (for grading scales for flare/cells and vitreal hemorrhage density; see [Appendix 12](#))
- Dilated binocular indirect high-magnification ophthalmoscopy

In addition, examinations will also be performed for patients in the Implant treatment arms after Implant insertion in the study eye, and then on Days 2, 7 ( $\pm 2$  days), and 14 ( $\pm 2$  days) after the Day 1 visit; afterward, dilated ophthalmoscopy examinations will be performed at each monthly visit to monitor the Implant placement, to evaluate visible clogging of the RCE tip, and to evaluate other Implant problems.
- Finger counting test, followed by hand motion and light perception tests (as applicable) performed within 15 minutes following Implant refill or ITV ranibizumab for the study eye only by the treating physician
- After each treatment, the patients will remain in the office or in the surgical center (as applicable) for approximately 40 minutes. If there are no safety concerns 40 ( $\pm 10$ ) minutes following treatment, the patient will be allowed to leave. If any safety concerns or immediate toxicity is noted, the patient will remain and will be treated according to the designated physician's clinical judgment. If applicable, the adverse event and the adverse event treatment must be reported on the appropriate eCRF page.

- Additional non-invasive ocular assessments may be performed by the Investigator to explore patient factors related to the Implant surgical procedures, regardless of whether a safety event occurred in a particular patient or not. Results of the additional ocular assessments will be forwarded to the Sponsor for evaluation and/or storage.

#### **4.6.5 Ocular Imaging**

Note: All ocular images will be forwarded to the central reading center for grading and/or storage, starting from the screening visit. See central reading center manual for details.

The following ocular images of both eyes will be collected from all study patients:

- Fundus photographs (see [Appendix 14](#))
- Lens photograph (fundus reflex photograph)
- Fluorescein angiograms (to be performed after laboratory samples are obtained; see [Appendix 15](#))
- SD-OCT scans (Heidelberg; see [Appendix 16](#))
- Fundus autofluorescence (Heidelberg; see [Appendix 13](#))

The following ocular images of both eyes will be collected only from patients in the Implant treatment arms from sites that have a Humphrey Visual Field machine and will be forwarded to the reading center for evaluation and/or storage:

- Visual field testing (Humphrey Automated Visual Field testing using Swedish interactive threshold algorithm Fast 24-2 protocol)

The following ocular images will be collected only from the study eye of patients in the Implant treatment arms and forwarded to the reading center for evaluation and/or storage:

- External photographs (high-magnification Implant and conjunctiva, scleral surface; see [Appendix 17](#))
- Implant photograph (high-magnification Implant in the eye, through dilated pupil; see [Appendix 17](#))

The following ocular images of both eyes will be collected from all study patients at selected sites that have OCT angiography equipment:

- OCT angiography (Optovue; see [Appendix 18](#))

Additional non-invasive ocular assessments (e.g., ocular B-scan ultrasonography or ultrasound biomicroscopy) may be performed by the Investigator to explore patient factors related to the Implant surgical procedures, regardless of whether a safety event occurred in a particular patient or not.

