## **6.5 SAFETY ANALYSES**

All patients receiving at least one study treatment will be included in the safety analysis.

Counts and incidence rates by treatment group for the following safety endpoints will be provided:

- Ocular and non-ocular adverse events and serious adverse events
- "Prespecified RPDS-associated adverse events" (see Section 6.5.1)
- Positive serum antibodies to ranibizumab

For "prespecified RPDS-associated adverse events", the incidence in all implant arms patients will also be summarized.

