### **6.5.1 Adverse Events**

Verbatim descriptions of treatment-emergent adverse events will be mapped to thesaurus terms. Treatment-emergent adverse events will be defined as events beginning during or after surgical insertion/explantation of the Implant or the first ranibizumab ITV injection through the completion of the study or until a patient discontinues prematurely. Adverse events will be tabulated by body system, high-level term, and preferred term. Separate summaries will be prepared for non-ocular and ocular adverse events, with events in the study eye and fellow eye summarized separately. Serious adverse events will be summarized similarly. Adverse events leading to discontinuation from the study or treatment will be listed and tabulated.

ADEs are adverse events that are considered to be related to the RPDS and to the use of the RPDS. Of particular interest are the following "Prespecified RPDS-associated adverse events":

- Vitreous hemorrhage associated with a >30-letter decrease of BCVA on ETDRS chart compared with the last assessment of BCVA prior to the onset of vitreous hemorrhage lasting > 1 month
- Reduced VA (> 30 letters loss from previous scheduled visit)
- Traumatic cataract
- Endophthalmitis
- Damage to sclera
- Retinal detachment
- Interference of the Implant with visual field

In addition to the "Prespecified RPDS-associated adverse events", any other ocular adverse events and serious adverse events attributed by the investigator to the:

1) Implant insertion procedure, 2) Implant refill procedure, 3) Implant explantation procedure, and 4) study drug, will be reported.

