**Appendix 1**  
**Schedule of Assessments for Implant Arms: Screening, Randomization, Day 1, Month 1 through Month 9, Month X, Safety Visits, and Final/Early Termination Visits (cont.)**

Assessment	Screen a ≥7 days after RBZ tx	Rand b ≥28 and ≤37 days after RBZ tx	Day				Month									Month X Visit d	Safety Visit c	Final/ ET e	
			1 b	2 c	7 c	14 c	1	2	3	4	5	6	7	8	9				
Window (Days)				±0	±2	±2	±7	±7	±7	±7	±7	±7	±7	±7	±7	±7	±7	See footnote c	See footnote e
Optional plasma (EDTA) sample for candidate biomarkers		x								x						x			
Optional aqueous humor sample r						Obtain prior to or immediately following one or more refills and at the safety visit 7 days post refill													
BCVA testing (starting at 4 m)	x	x		x	x	x	x	x	x	x	x	x	x	x	x	x	x	x	x
Low luminance BCVA testing s	x	x		x	x	x	x	x	x	x	x	x	x	x	x	x	x	x	x
Visual Field testing (Humphrey 24-2) t		x u														x			x
Axial Length Measurement (ultrasound or optical biometry) v		x u																	
Intraocular pressure (IOP) w	x	x	x x	x	x	x	x	x	x	x	x	x	x	x	x	x	x	x	x

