## **Appendix 1**

### **Schedule of Assessments for Implant Arms: Screening, Randomization, Day 1, Month 1 through Month 9, Month X, Safety Visits, and Final/Early Termination Visits (cont.)**

- o Collect serum PK sample for ranibizumab concentration from Implant treatment arms patients  $\geq$  60 minutes post treatment on Day 1 visit (if possible) and then on Days 2, 7 ( $\pm$ 2 days), and 14 ( $\pm$ 2 days) after Day 1 visit; afterwards collect serum PK sample 1 and 7 ( $\pm$ 2) days after each refill. Collect a serum PK sample at the early termination visit if applicable. Note: for patients who are unable to visit the clinic for the PK sample collection 1 day after each Implant refill, provision will be made for this timepoint sample collection to be collected at their home. Alternatively, the sample may be collected 2 days after the refill. Training will be provided to site staff on how to perform this task. The sample will be sent to a central laboratory.
- p Perform only if possible.
- q Obtain serum anti-ranibizumab antibody sample from the Implant treatment arms patients prior to the study treatment and prior to fluorescein angiography (if applicable) on the Randomization visit, Visits Day 14, Month 1, 3, 6, and 9 and at the early termination visit if applicable.
- r If a patient has consented to this optional sample collection, obtain the aqueous humor sample prior to or immediately following one or more refills and at the Day 7 safety visit post refill.
- s Perform low luminance BCVA testing after standard BCVA testing.
- t Perform only if you have the Humphrey Visual Field machine at your site. In addition to the listed timepoints, this testing will be performed any time the patient reports a new defect of the peripheral vision.
- u If it cannot be performed during Randomization, this testing must be performed on a subsequent day but before Day 1.
- v Perform only if you have ultrasound or optical biometry capability at your site.
- w Perform pre-treatment.
- x Should be performed in the surgical center using Tono-Pen tomometry prior to the Implant insertion surgery.

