#### **5.4 RISKS AND ANTICIPATED ADVERSE DEVICE EFFECTS THAT ARE TO BE ASSESSED**

At the end of the study, the incidence of “Prespecified RPDS-associated AEs” will be compared between subjects receiving ranibizumab from the Implant and the control subjects receiving ranibizumab as ITV injections:

- Vitreous hemorrhage associated with a > 30-letter decrease in BCVA on the ETDRS chart compared with the last assessment of BCVA prior to the onset of vitreous hemorrhage lasting >1 month
- Reduced VA (>30-letter loss from previous scheduled visit)
- Traumatic cataract
- Endophthalmitis
- Damage to sclera
- Retinal detachment
- Interference of the Implant with visual field

In addition, ocular AEs and serious adverse events (SAEs) attributed by the investigator to: 1) the Implant insertion procedure, 2) the Implant refill procedure, 3) Implant explantation procedure, and 4) the Implant and other RPDS components, will be reported.

Please also refer to the protocol Section 6.5.1.

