#### **4.6.4 Ocular Assessments**

Results of the following ocular assessments will be summarized by timepoint and by eye (study vs. fellow), as applicable, using descriptive summaries: intra-ocular pressure, fluorescein angiography, and fundus photography. Changes from baseline for selected ocular assessments will be tabulated. The presence of intra-ocular inflammation and vitreous hemorrhage, as determined from the slit-lamp examination, will be tabulated by grade (according to grading scales for flare/cells and vitreous hemorrhage density in the appendix of the study protocol). The presence of retinal break or detachment as determined from ophthalmoscopy will be tabulated.

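### Humphrey visual fields are collected in some Implant patients but named in no planned summary, and the SAP's device-event list omits visual field interference, so a low count cannot tell tested-and-clear from never-tested

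*Protocol*

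**What the plan says.** **Who is tested.** Protocol 4.6.5 restricts Humphrey 24-2 testing: these data "will be collected only from patients in the Implant treatment arms from sites that have a Humphrey Visual Field machine". Both eyes are tested, and the results go to the reading center, which may evaluate them or only store them. The Appendix 1 row "Visual Field testing (Humphrey 24-2" places the test at randomization, once on study (apparently Month 9; the column alignment is unclear in the copy reviewed) and at the final or early termination visit. Its footnote t opens "Perform only if you have the Humphrey Visual Field machine at your site" and continues "In addition to the listed timepoints, this testing will be performed any time the patient reports a new defect of the peripheral vision". The ITV schedule in Appendix 2 has no field test.

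**The event.** Protocol 6.5.1 lists "Interference of the Implant with visual field" among the prespecified RPDS-associated adverse events, without a test-based definition. For these events Protocol 6.5 adds that "the incidence in all implant arms patients will also be summarized". Section 5.4 of the device Clinical Investigation Plan (CIP, Appendix 21) says that their incidence "will be compared between subjects receiving ranibizumab from the Implant and the control subjects receiving ranibizumab as ITV injections". CIP 7.5 makes their characterization part of the device safety criterion.

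**The analysis.** Protocol 6.5.5 and SAP 4.6.4 name the same three ocular assessments; in the SAP they are summarised "using descriptive summaries: intra-ocular pressure, fluorescein angiography, and fundus photography". SAP 2.1 states that the SAP replaces the protocol's analysis plan. SAP 2.2.3 still lists the prespecified device events as a safety outcome, but the nine device-related terms tabulated under SAP 4.6 do not include visual field interference.

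**The concern.** Visual field interference is one of a short list of risks that the sponsor singled out for the device. The only perimetry in the trial is done in an unspecified subset of Implant patients, and no planned output names its results. Under the governing SAP, the event would surface only within the general ocular adverse event and adverse device effect tables, with rates by dose arm and pooled over all Implant patients.

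Suppose the final table shows none or very few such events. The reader cannot tell how many patients had a baseline and a later field and were clear, and how many were never examined for it. An asymptomatic peripheral defect at a site without the machine has no scheduled functional test that would reveal it. On the wording of footnote t, even the symptom-triggered test depends on the site owning the machine. At stake is the interpretability of one named device risk, and field data that patients have already given.

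**Working it through.** **No plan figure to reproduce.** The documents state no expected rate, precision or sample size for visual field interference.

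**Inputs**
- Planned Implant patients: 3 × 60 = 180 (Protocol synopsis and 3.1.3), before removal of untreated patients and of the site excluded under SAP 4.1.
- f, the share of Implant patients at sites with a Humphrey machine: not given; varied from 0.25 to 1.
- s0, the share of true events recorded as adverse events without a field test: not given; varied from 0 to 1.
- Assumed: every event in a tested patient is found and recorded, and the true rate p is the same at equipped and unequipped sites.

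**Formula.** Of N patients, fN are tested and yield fNp recorded events. The other (1 − f)N yield (1 − f)Np·s0. Dividing by the true count Np gives

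recorded/true = f + (1 − f)s0.

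| f | s0 = 0 | s0 = 0.5 | s0 = 1 |
|---|---|---|---|
| 0.25 | 0.25 | 0.625 | 1.00 |
| 0.50 | 0.50 | 0.75 | 1.00 |
| 0.75 | 0.75 | 0.875 | 1.00 |
| 1.00 | 1.00 | 1.00 | 1.00 |

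The ratio is below 1 only if f < 1 and s0 < 1. For scale, with an assumed true rate of 5% (0.05 × 180 = 9 events) and f = 0.5, the expected recorded counts are 9 × 0.50 = 4.5, 9 × 0.75 = 6.75 and 9 × 1.00 = 9.

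**What a zero count would support.** The plan computes no upper limit for this event. If someone did, the one-sided 95% limit with no events is 1 − 0.05^(1/n):
- n = 180 (all tested): 1.65%
- n = 90 (f = 0.5): 3.27%
- n = 45 (f = 0.25): 6.44%

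The number tested therefore decides what a zero count means, and no planned output shows it.

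**Lists side by side.** The event appears in Protocol 6.5.1 and in CIP 4.2, 5.4 and 14.7. SAP 2.2.3 refers to the prespecified events as a group. The tabulated list under SAP 4.6 has nine terms (vitreous hemorrhage, endophthalmitis, retinal detachment, four conjunctival terms, hyphema and cataract) and none concerns the visual field. The SAP therefore names an outcome group that its own table does not fully cover.

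**The case against.** The best case for the plan is that detection does not depend on the machine. The event is an adverse event term. Adverse events are sought at every contact in all arms (Protocol 5.3.1). Patients are called after each treatment and asked about reduced vision and new ocular symptoms (Protocol 3.1, 5.1). Implant patients have monthly dilated ophthalmoscopy to check Implant placement and problems (Protocol 4.6.4). A patient who reports a new peripheral defect at an unequipped site has a recordable event without any field test. This stands. It confines the gap to interference that causes no complaint and is not visible on examination. Protocol 5.3.2 calls for non-directive questioning and ophthalmoscopy does not measure field function, so that gap is real but of unknown size.

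Several stronger readings are tempting and are not supported:
- A reader might infer that the risk is shown to be understated. It is not: s0 could be close to 1, and the table then gives ratios close to 1. Multiplying a true rate by the share tested is the s0 = 0 extreme.
- A reader might infer that leaving ITV patients untested causes understatement. An eye without an Implant cannot have Implant interference, so the control rate is zero by definition. Testing only Implant patients cannot lower their rate or the difference between arms.
- A reader might take 1.65% as a limit that the plan quotes. The plan provides counts and incidence rates only.
- A reader might treat the fellow eye as a clean within-patient control. It may itself have nAMD and receive ranibizumab (Protocol 3.1, 4.5.1).

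It can also be said that Protocol 6.5.5 and SAP 4.6.4 tabulate changes for selected ocular assessments, which could include fields, and that the reading center manual is not available here. That is fair, but an unnamed selection does not commit anyone to the analysis. Finally, this is one descriptive safety term in an exploratory Phase II trial, so the point has no bearing on the primary analysis.

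**Conclusion.** The point holds as a reporting gap. Field data are collected in an unspecified subset of Implant patients and named in no planned summary, and the SAP keeps the prespecified device events as an outcome while omitting this one from its tabulated list. As planned, a low or zero count cannot be read as evidence of absence, and asymptomatic interference may be under-counted.

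The documents do not determine how large the under-count is. The recorded-to-true ratio lies between f and 1; at f = 0.5 that is 0.50 to 1.00. This range rests on assumed f and s0, complete detection and recording where tested, and equal true rates across sites. The CIP comparison with ITV is uninformative for this event rather than biased, because the event needs an Implant. The improvement is worth making because it costs almost nothing.

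**What to change.** 1. In SAP 4.6.4, add a descriptive summary of visual field change from randomization to the on-study test and to the final test, in tested Implant patients, by study eye and fellow eye, with the number tested at each time. Present the fellow eye as a descriptive reference only. Final tests will not all follow explantation, because patients who enter the Extension Study keep the Implant (Protocol 4.6.10.5); label the summary accordingly.
2. Report visual field interference among Implant patients with a baseline and at least one later field test, beside the all-Implant rate.
3. Reconcile the SAP 4.6 device-event list with the prespecified list in Protocol 6.5.1, CIP 5.4 and SAP 2.2.3 so that the event is tabulated. In CIP 5.4, mark it *not applicable* for the ITV arm.

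The cost is one table, one added row with its own denominator, and a few sentences in the SAP and CIP. No visits, tests or patients are added, and the primary analysis is unchanged.
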